The study will close after the last enrolled subject completes 5 year follow up. The duration of the study will be 6.5 years.

Study Population: Patients with Stage 3b/4 NSCLC (squamous or non-squamous histology) who have experienced disease progression or recurrence during or after at least one systemic therapy for advanced or metastatic disease. Subjects must meet all eligibility criteria specified in [Section 3.3](#) of the protocol.

Study Assessments: Main assessments include: Incidence, severity and outcome of select adverse events, and specific related laboratory abnormalities. Exploratory assessments include incidence and severity of all adverse events, laboratory abnormalities, efficacy measures, patient reported outcomes [REDACTED].

Statistical Considerations:

Sample Size: In order to further characterize the frequency and outcome of the rather infrequent treatment related select adverse of high grade (Grade 3-5), the current study will treat approximately 780 subjects with nivolumab. This sample size will allow for estimating an incidence rate of 0.5% (n=4 subjects with events) with a 95% CI (confidence interval) of (0.14%, 1.31%), or an incidence rate of 2% (n=16 subjects with events) with a 95% CI of (1.18%, 3.31%).

This study also includes a randomization step reserved to subjects who received nivolumab for 1 year (52 weeks). In MDX1106-03, 27% of NSCLC subjects (10 of 37) were still on treatment [95% CI of (12.7%, 41.3%)] at Week 48. In the present study any subjects (all subgroups included) who are still benefiting from therapy after 52 weeks (estimated to be between 99 and 322 subjects) will be randomized in order to continue treatment without any change in Cohort A, or to discontinue treatment in Cohort B, respectively.

Endpoints: The primary objective of the study will be assessed by measuring the incidence for high grade (Grade 3-4 and Grade 5) treatment related select adverse events.

The select adverse events of interest are the following: pneumonitis, interstitial nephritis, diarrhea/colitis, hepatitis, rash, endocrinopathies, and hypersensitivity/infusion reaction events.

The secondary objective of the study will be assessed by measuring the following:

- incidence for high grade (Grade 3-4 and Grade 5) select adverse events
- median time to onset, median time to resolution (Grade 3-4) of the select adverse events

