Nivolumab-related AEs are mostly thought to be due to the effects of inflammatory cells on specific tissues and management of these AEs may require special consideration. Among the safety events observed, a few categories were identified as likely to be due to an immune mechanism. These select AEs may require more frequent monitoring and/or unique intervention (immunosuppressants or hormonal replacement), and are addressed in a consistent and unified manner throughout the program by specifically designed safety algorithms (See [Appendix 2](#) for Management Algorithms).

Categories of “select AEs” have been created to group together the most common and impactful preferred terms (PTs) by organ category, providing a better estimate of the frequency of similar kinds of organ-related AEs instead of using PTs only. These select adverse events are further defined as follows:

- may differ from or be more severe than AEs caused by non-immunotherapies

- may require unique (non-standard) intervention such as immunosuppressants (or hormone replacement therapy), and
- early recognition and management may mitigate severe toxicity.

The preferred terms included in the ‘select AEs’ category are those that are expected to be most commonly used to describe pneumonitis, interstitial nephritis, diarrhea/colitis, hepatitis, rash, and endocrinopathies. Hypersensitivity/infusion reactions are also considered a select AE category to facilitate the pooling of the most relevant preferred terms for analyses of hypersensitivity/infusion reaction events, and not because such events fit the criteria for select AEs listed above.

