3 INVESTIGATIONAL PLAN

3.1 Study Design and Duration

In this safety study of nivolumab monotherapy, subjects will undergo screening evaluations to determine eligibility within 28 days prior to first dose. Eligible subjects will be treated with nivolumab administered intravenously over 30 minutes at 3 mg/kg every two weeks. Each

14 day dosing period will constitute a cycle. After 1 year (52 weeks) of treatment all subjects who are still on treatment will be randomized (1:1) to one of the two cohorts, Cohort A or Cohort B.

- Cohort A: Subjects randomized to Cohort A will continue to receive treatment until disease progression, unacceptable toxicity, or withdrawal of informed consent.
- Cohort B: Subjects randomized to Cohort B will discontinue treatment at 1 year (52 weeks). After randomization, subjects will remain on the study and will follow all study assessments [REDACTED]. Upon progression, subjects can receive retreatment.

Subjects who are retreated can continue to receive study drug until further progression, unacceptable toxicity, or withdrawal of informed consent.

Study treatment can continue beyond initial investigator assessed progression, as specified in criteria presented in [Section 4.3.4 Treatment Beyond Disease Progression](#). The study will close after the last enrolled subject completes 5 year follow up.

The study will enroll subjects into 4 subgroups as detailed in [Table 3.1-1](#).

Enrollment will open first to subgroup 1 only. A decision to open enrollment for each of the other subgroups 2-4 will be dependent upon the sponsor review of data from the ongoing Phase 2 and 3 studies for each patient population. The decision will take into account the overall risk/benefit profile for each patient population and the determination will be made whether or not to collect additional safety and efficacy data to supplement that already collected.

At the time of Protocol Amendment 01 (June 2014), all subgroups were opened.

Protocol Amendment 03 (November 2014) allowed for continued enrollment beyond 780 subjects in two of the study subgroups. However, as of Protocol Amendment 04 (December 2014), enrollment under Amendment 03 will stop, but enrollment will continue until 500 additional subjects are treated. Enrollment will continue until a total of 1280 subjects are treated.

[REDACTED]

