Under Protocol Amendment 04, all subjects will receive nivolumab by IV infusion administered over 30 minutes, including new and existing subjects enrolled in the study, including subjects enrolled under Amendment 02.

The study design schematic is presented in [Figure 3.1-1](#).

Figure 3.1-1: Study Design Schematic

[figure not shown]

Table 3.1-1: Staggered Enrollment by Patient Subgroup

Histology (Subgroup Number) ^a	Disease Criteria	Staggered Enrollment ^{b,d}
Squamous (Subgroup 1) ^c	
 Failed two or more prior therapies PS 0-1 Subjects with treated CNS metastases requiring no corticosteroids, or on a stable or decreasing dose of < 10 mg daily prednisone (or equivalent) are allowed 	Opens at study start
Squamous (Subgroup 2)	
 Failed only one prior therapy PS 0-1 Subjects with treated CNS metastases requiring no corticosteroids, or on a stable or decreasing dose of \leq 10 mg daily prednisone (or equivalent) are allowed 	Yes
Nonsquamous (Subgroup 3)	
 Failed at least 1 prior therapy PS 0-1 Subjects with treated CNS metastases requiring no corticosteroids, or on a stable or decreasing dose of \leq 10 mg daily prednisone (or equivalent) are allowed 	Yes
Squamous ^c and nonsquamous (Subgroup 4)	
 Failed at least 1 prior therapy PS 2 Subjects with treated CNS metastases requiring no corticosteroids, or on a stable or decreasing dose of < 10 mg daily prednisone (or equivalent) are allowed 	Yes

^a Subgroup number does not necessarily reflect the order in which the subgroups will be allowed to enroll.

^b Staggered enrollment of subgroups will depend upon the sponsor review of data from the ongoing studies for each patient population. The decision will take into account the overall risk/benefit profile for each patient population and the determination for additional data to further assess the risk/benefit profile.

^c Per Amendment 03 (November 2014), enrollment continued for subjects with squamous histology with at least 2 line of prior therapy subjects have been enrolled. Enrollment under Amendment 03 will stop when Amendment 04 starts.

^d Per Protocol Amendment 04 (December 2014), an additional 500 subjects will be treated in the study. The enrollment of subjects in all subgroups will continue until a total of 1280 subjects are treated on study.

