8 STATISTICAL CONSIDERATIONS

8.1 Sample Size Determination

In general, for nivolumab monotherapy, the safety profile to date is similar across tumor types, while select treatment related adverse events of high grade (Grade 3-4) are rather uncommon. Their overall incidence was 6% in a previous Phase 1 trial that tested nivolumab at doses between 0.1 mg/kg to 10 mg/kg in 306 subjects with different recurrent or refractory malignancies (MDX-03). The incidence observed for similar AEs 0% in NSCLC subjects (n=129) was 0% for skin and renal AEs, and endocrinopathies; 1% gastro-intestinal, hepatic and infusion reaction AEs, and 2% for pulmonary events.⁷

In order to further characterize the frequency and outcome of such apparently infrequent safety events, the current study will treat with nivolumab approximately 780 subjects who have advanced or metastatic NSCLC and have progressed during or after at least one prior systemic regimen. This sample size will allow for estimating an incidence rate of 0.5% (n=4 subjects with events) with a 95% CI (confidence interval) of (0.14%, 1.31%), or an incidence rate of 2% (n=16 subjects with events) with a 95% CI of (1.18%, 3.31%). Furthermore, the sample size will allow for enough events such that the outcome of these rare events can be characterized.

Estimated 95% confidence intervals for various event rates for an overall population of 780 subjects, and for different size subpopulation are described in [Table 8.1-1](#).

Table 8.1-1: Estimated Incidence Rates and 95% Confidence Intervals for the Overall Study Population and Subpopulations

Sample Size	Incidence Rate (%)	Lower 95% CI (%)	Upper 95% CI (%)
780	0.5	0.14	1.31
780	1.0	0.44	2.01
780	2.0	1.18	3.31
780	5.0	3.58	6.77
400	1.0	0.27	2.54
400	2.0	0.87	3.90
400	5.0	3.08	7.62
300	1.0	0.21	2.89
300	2.0	0.74	4.30
300	5.0	2.83	8.11
200	1.0	0.12	3.57
200	2.0	0.55	5.04
200	5.0	2.42	9.00
100	2.0	0.24	7.04
100	5.0	1.64	11.28
100	10.0	4.90	17.62

CI: confidence interval

SAS 9.2 was used to generate the 95% exact confidence intervals.

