8.1.1 Sample Size at Randomization

This study also includes a randomization step reserved to subjects who received nivolumab for 1 year. In MDX1106-03, 27% of NSCLC subjects (10 of 37) were still free from disease progression at 48 weeks [95% CI of (12.7%, 41.3%)]. In the present study any subjects (all subgroups included) who are still benefiting from therapy after 1 year (estimated to be between 99 and 322 subjects) will be randomized in order to continue treatment without any change in Cohort A (until progression, toxicity or withdrawal of consent), or to discontinue treatment in Cohort B, respectively. In the latter subjects will have the option of retreatment should progression occur.

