8.2 Populations for Analyses

- All enrolled subjects: all subjects who signed an informed consent form and were registered into the IVRS.
- All treated subjects: all subjects who received any nivolumab. This is the primary population for safety and efficacy analyses. Subpopulation analyses will be conducted by

tumor histology (SQ or NSQ), by subject subgroups (subgroup 1 to 4), and for Cohorts A and B.

- All randomized subjects: all subjects who were randomized to Cohort A or B after completing 1 year of treatment.
- All response evaluable subjects: all treated subjects who have baseline and at least one on-study evaluable tumor measurement.
- [REDACTED]
- [REDACTED]

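### The trial will treat 1280 subjects, but the sample-size text still gives the confidence intervals and the number randomised for 780.

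*Combined protocol and SAP*

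**What the plan says.** **Number treated.** Section 3.1 says: "Enrollment will continue until a total of 1280 subjects are treated". Footnote d of Table 3.1-1 agrees: "The enrollment of subjects in all subgroups will continue until a total of 1280 subjects are treated on study". The synopsis design text also gives 1280. Section 1.1.1 opens with about 780 and later adds 500 under Amendment 04.

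**Sample-size text.** Section 8.1 says "the current study will treat with nivolumab approximately 780 subjects who have advanced or metastatic NSCLC", and the synopsis sample-size paragraph says "the current study will treat approximately 780 subjects with nivolumab". Table 8.1-1 takes 780 as its overall population and gives exact 95% intervals for incidences of 0.5%, 1%, 2% and 5%.

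**Number randomised.** Section 8.1.1 and the synopsis give the number reaching the one-year randomisation as "estimated to be between 99 and 322 subjects". The basis is 10 of 37 subjects in study MDX1106-03 (27%, 95% CI 12.7% to 41.3%). Section 8.1.1 says these subjects "were still free from disease progression at 48 weeks". The synopsis describes the same 10 of 37 as still receiving treatment at Week 48.

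**Analysis.** Section 8.2 defines all treated subjects as those given any nivolumab and adds: "This is the primary population for safety and efficacy analyses". Section 8.4.2 plans the number and percentage with a high-grade treatment-related select adverse event in that population, tabulated by system organ class and preferred term.

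**The concern.** The study tests no hypothesis about its primary endpoint. It estimates an incidence, so the interval table is the main quantitative statement of what its size delivers. When the total rose from 780 to 1280, the design sections were updated and the sample-size sections were not. The synopsis now carries both totals, and the legible text of Section 8 mentions neither 1280 nor the added 500.

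A reader who relies on Section 8 is misinformed about the precision of the primary estimate and about the expected size of the Cohort A versus Cohort B comparison.

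There are two connected weaknesses:

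- The proportion behind the randomisation estimate is described in two ways that are not equivalent. Section 4.3.4 allows treatment beyond progression, so being on treatment and being progression-free can differ.
- Section 8.1 justifies the size through confidence intervals and cites incidence per organ category. Section 8.4.2 names no interval and no summary per category. Section 1.1 explains that the categories were created for "providing a better estimate of the frequency of similar kinds of organ-related AEs instead of using PTs only".

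**Working it through.** **Inputs.** Total treated: 1280 (Section 3.1; Table 3.1-1, footnote d) or 780 (Section 8.1; synopsis). Interval method: exact 95% (note to Table 8.1-1). Proportion reaching one year: 10 of 37, 12.7% to 41.3% (Section 8.1.1).

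**Step 1: reproduce the stated intervals.** For x events in n subjects, the Clopper-Pearson limits are:

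- lower = 2.5% quantile of Beta(x, n − x + 1)
- upper = 97.5% quantile of Beta(x + 1, n − x)

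Take x as n times the incidence, rounded to a whole number. At n = 780 this gives 4, 8, 16 and 39 events. All 16 rows of Table 8.1-1 reproduce to two decimals. The table is correct for 780.

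**Step 2: repeat at n = 1280.** Expected events are 6.4, 12.8, 25.6 and 64.

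| Incidence | 780, as stated | 1280 | Width at 780 | Width at 1280 | Change in width |
|---|---|---|---|---|---|
| 0.5% | 0.14% to 1.31% (4 events) | 0.17% to 1.02% (6 events, 0.47%) | 1.168 | 0.845 | −27.6% |
| 0.5% | as above | 0.22% to 1.12% (7 events, 0.55%) | 1.168 | 0.903 | −22.6% |
| 1% | 0.44% to 2.01% (8 events) | 0.54% to 1.73% (13 events) | 1.567 | 1.189 | −24.1% |
| 2% | 1.18% to 3.31% (16 events) | 1.33% to 2.96% (26 events) | 2.133 | 1.631 | −23.5% |
| 5% | 3.58% to 6.77% (39 events) | 3.87% to 6.34% (64 events) | 3.193 | 2.469 | −22.7% |

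Widths are in percentage points. Two counts are shown at 0.5% because 6.4 is not a whole number and neither 6 nor 7 gives exactly 0.5%. Seen from the other side, the stated intervals at 1%, 2% and 5% are 29 to 32% wider than those for 1280.

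**Step 3: reproduce the number randomised.** The normal-approximation interval for 10/37 is 0.270 ± 1.96 × √(0.270 × 0.730 / 37), which is 12.7% to 41.3%, as stated. Then:

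- 780 × 0.127 = 99.1
- 780 × 0.413 = 322.1

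These are the stated 99 and 322, so the range was built on 780.

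**Step 4: repeat at 1280.** Section 3.1 randomises every subject still on treatment at 52 weeks, so the projection scales with the total treated:

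- 1280 × 0.127 = 162.6
- 1280 × 0.413 = 528.6

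The range is about 163 to 529. The stated range is too low by 1 − 780/1280 = 39.1%. Conversely, 99/1280 = 7.7% and 322/1280 = 25.2%. Kept beside a total of 1280, the stated range implies a proportion that contradicts the 12.7% to 41.3% quoted in the same section.

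**The case against.** The strongest reply is that little depends on these figures. There is no power claim, hypothesis test or formal interim analysis, and no enrolment rule uses the intervals. The error makes the trial look less precise than it is. Section 1.1.1 gives the 780 basis and the added 500 in one place, and says the 500 are to continue safety data collection and characterise the outcome of immune-mediated effects. So 780 could be read as the original justification and the 500 as an extension, for which one bridging sentence would do. All of this limits the severity. It does not remove the contradiction: Section 8.1 says in the present tense that the current study will treat about 780, and no legible text in Section 8 keeps the 500 out of the primary population.

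Other points on that side stand:

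- This is a failure to update, not a miscalculation. Only the four 780 rows of Table 8.1-1 are out of date. The twelve rows for 400, 300, 200 and 100 do not depend on the total.
- The randomisation range rests on 37 subjects and is very wide. The stated and rescaled ranges overlap from 163 to 322.
- Section 1.1.1 also uses the 27% figure (on treatment after 48 weeks), and Section 1.1.2.1 gives the same 10 of 37 as on treatment after one year. Harmonising only the synopsis and Section 8.1.1 would leave a discrepancy.
- The study schematic, Figure 3.1-1, is not visible in the text available. It may carry updated numbers, but that would not correct Section 8.1.1.
- The missing interval and category summary in Section 8.4.2 is a separable request and does not support the main finding.

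**Conclusion.** The concern holds. Current protocol text gives two totals for the same trial, and the precision statement and randomisation projection belong to the smaller one. At 1280 the intervals for 1%, 2% and 5% incidence are 23 to 24% narrower than stated, and the projected number randomised is about 163 to 529 instead of 99 to 322.

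The trial is not under-sized, and no analysis is invalidated. The Cohort A versus Cohort B comparison is exploratory with no stated power, so the low projection affects planning and not validity. The correction should be made but is not critical.

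The interval figures assume that all 1280 treated subjects enter the primary analysis, as Section 8.2 says. The 163 to 529 assumes that the added 500 reach one year at the same 12.7% to 41.3%, and, on the synopsis and Section 8.1.1 description, applies a 48-week proportion to a 52-week randomisation.

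**What to change.** 1. Restate Section 8.1, the four 780 rows of Table 8.1-1 and the synopsis sample-size paragraph for 1280, using the intervals above and showing event counts. Rounding to the nearest whole number gives 6 events (0.47%) for the 0.5% row. The 780 figures may stay if labelled as the original basis. Align the opening of Section 1.1.1.
2. In Section 8.1.1 and the synopsis, give the number randomised as about 163 to 529, with the two assumptions stated.
3. Check the 10 of 37 against its source. Describe both the outcome (on treatment or progression-free) and the time point (48 weeks or one year) the same way in the synopsis and Sections 1.1.1, 1.1.2.1 and 8.1.1.
4. As an inexpensive addition to Section 8.4.2, attach exact 95% intervals to the overall primary incidence and to the incidence in each select adverse event category. Keep the system organ class and preferred term table as detail. Sections 8.4.4.2 and 8.4.4.3 already name Clopper-Pearson intervals for exploratory endpoints.

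The cost is wording in the four sample-size places, small matching edits in Sections 1.1.1 and 1.1.2.1, four recalculated table rows and one extra summary table. No patients, visits or data are added.

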8.1.1 Sample Size at Randomization

This study also includes a randomization step reserved to subjects who received nivolumab for 1 year. In MDX1106-03, 27% of NSCLC subjects (10 of 37) were still free from disease progression at 48 weeks [95% CI of (12.7%, 41.3%)]. In the present study any subjects (all subgroups included) who are still benefiting from therapy after 1 year (estimated to be between 99 and 322 subjects) will be randomized in order to continue treatment without any change in Cohort A (until progression, toxicity or withdrawal of consent), or to discontinue treatment in Cohort B, respectively. In the latter subjects will have the option of retreatment should progression occur.

8.2 Populations for Analyses

- All enrolled subjects: all subjects who signed an informed consent form and were registered into the IVRS.
- All treated subjects: all subjects who received any nivolumab. This is the primary population for safety and efficacy analyses. Subpopulation analyses will be conducted by

tumor histology (SQ or NSQ), by subject subgroups (subgroup 1 to 4), and for Cohorts A and B.

- All randomized subjects: all subjects who were randomized to Cohort A or B after completing 1 year of treatment.
- All response evaluable subjects: all treated subjects who have baseline and at least one on-study evaluable tumor measurement.
- [REDACTED]
- [REDACTED]

8.3 Endpoints

8.3.1 Primary Endpoint(s)

The primary objective of the study will be assessed by measuring the incidence for high grade (Grade 3-4 and Grade 5) treatment related select adverse events.

8.3.2 Secondary Endpoint(s)

The secondary objective of the study will be assessed by measuring the following:

- incidence for high grade (Grade 3-4 and Grade 5) select adverse events
- median time to onset, median time to resolution (Grade 3-4)
- percentage of subjects who received immune modulating medication (e.g. corticosteroids, infliximab, cyclophosphamide, IVIG, and mycophenolate mofetil), or hormonal replacement therapy, the percentage of subjects who received ≥ 40 mg prednisone equivalents, total duration of all immune modulating medications given for the select event.

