The frequencies of these events in study MDX1106-03 (Phase 1 study; N = 306; heavily pre-treated subjects with different tumor types) are summarized in [Table 1.1-1](#). The treatment-related select AEs of Grade 3-4 observed to date are rather uncommon: 6% overall in study MDX1106-03, while their incidence per category varies between 0.3% and 2% (pulmonary AEs). Of note, the 10 mg/kg cohort had numerically greater frequency of such AEs compared with the other dose levels. In the NSCLC subjects treated in the study (n=129) the overall incidence of Grade 3-4 treatment-related select AEs was 5%: 0% for skin and renal AEs, and endocrinopathies; 1% gastrointestinal, hepatic, and infusion reaction AEs; and 2% for pulmonary events.⁷ Most high-grade events of special interest were observed to have resolved while addressed with systemic corticosteroids and/or other immunosuppressive agents. One exception was Grade 4 pneumonitis considered to have led to death of three subjects: two of them were treated at the 1 mg/kg dose level and had NSCLC and CRC, respectively; the third subject had NSCLC and was treated at the 10 mg/kg dose level.

Specific safety algorithms have been designed for the select categories of AEs, and are implemented in a unified manner in all current studies in the nivolumab program (See [Appendix 2](#) for Management Algorithms). These safety algorithms assist the diagnostic, the assessment of relatedness, and the management of the select AEs, also they are continuously evaluated and adjusted as experience accumulates. The current study will focus on improving precision around the frequency of high-grade select AEs, and on obtaining information on their outcome.

Table 1.1-1: Treatment-related Select Adverse Events by Treatment - All CTC Grades Reported in at Least 10 Treated Subjects in MDX1106-03

Preferred Term	0.1 mg/kg n=17		0.3 mg/kg n=18		1 mg/kg n=86		3 mg/kg n=54		10 mg/kg n=131		Total N=306	
	Any Grade	Grade 3-4	Any Grade	Grade 3-4	Any Grade	Grade 3-4	Any Grade	Grade 3-4	Any Grade	Grade 3-4	Any Grade	Grade 3-4
Any Select AE	8 (47)	1 (5.9)	9 (50)	0	42 (49)	3 (4)	23 (43)	2 (4)	58 (44)	13 (10)	140 (46)	19 (6)
Any Endocrinopathies	4 (24)	0	2 (11)	0	9 (11)	0	4 (7)	0	10 (8)	3 (2)	29 (10)	3 (1)
Endocrinopathies Thyroid	3 (18)	0	2 (11)	0	9 (11)	0	4 (7)	0	8 (6)	2 (2)	26 (9)	2 (1)
Blood TSH increased	2 (12)	0	1 (6)	0	2 (2)	0	2 (4)	0	4 (3)	1 (1)	11 (4)	1 (0.3)
Hypothyroidism	1 (6)	0	1 (6)	0	5 (6)	0	1 (2)	0	3 (2)	1 (1)	11 (4)	1 (0.3)

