1.3.2 Secondary Objectives

To estimate the incidence and characterize the outcome of all high grade (CTCAE v4.0 Grade 3-4 and Grade 5) select adverse events in subjects with advanced or metastatic NSCLC who have progressed during or after at least one prior systemic therapy and are treated with nivolumab monotherapy.

1.3.3 Exploratory Objective(s):

- To assess safety and tolerability of nivolumab, as measured by incidence and severity of AEs and specific laboratory abnormalities in all treated subjects, by tumor histology (SQ or NSQ), by subject subgroups, and in Cohorts A and B
- To estimate efficacy of nivolumab by measuring overall survival (OS), progression-free survival (PFS), objective response rate (ORR) based on investigator assessment, and duration of response (DOR) in all treated subjects, by tumor histology (SQ or NSQ), by subject subgroups, and in Cohorts A and B (OS, PFS and DOR only)
- To explore the evolution of Patient Reported Outcomes (PRO) using the Lung Cancer Symptoms Scale (LCSS) and EQ-5D instruments in all treated subjects, by subject subgroups, and in Cohorts A and B

- To estimate the proportion of subjects exhibiting disease-related symptom improvement by 12 weeks as measured by LCSS

- [REDACTED]
- [REDACTED]
- [REDACTED]

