8.4.3 Secondary Analyses

The number and percentage of subjects who report high grade (Grade 3-4 and Grade 5) select adverse events will be summarized for all treated subjects. High grade (Grade 3-4 and Grade 5) select adverse events will be tabulated using worst grade per NCI CTCAE v4.0 criteria by system organ class and Medical Dictionary for Regulatory Affairs (MedDRA) preferred term.

Additional descriptive statistics will include median values using the Kaplan-Meier (KM) product-limit method with 95% CI using Brookmeyer and Crowley method of time to onset and time to resolution, and will be presented for all treated subjects, by tumor histology (SQ or NSQ), by subject subgroups, and all randomized subjects for Cohorts A and B. Time to onset is calculated from first dosing date to the event onset date. If a subject never experienced the given AE, the subject will be censored at the last contact date. Time to resolution is calculated from the

AE onset date to AE end date. If an AE is ongoing at the time of analysis, the time to resolution will be censored at the last contact date.

Management of high-grade (CTCAE v4.0 Grade 3-4 and Grade 5) select adverse events will be characterized by measuring percentage of subjects who received immune modulating medication (or hormonal replacement therapy), percentage of subjects who received ≥ 40 mg prednisone equivalents, and total duration of all immune modulating medications given for the event, in all treated subjects who have experienced high-grade (CTCAE v4.0 Grade 3-4 and Grade 5) select adverse events, by tumor histology (SQ or NSQ), and also by subject subgroups, and all randomized subjects in Cohorts A and B.

8.4.4 *Exploratory Analyses*

8.4.4.1 *Safety Analyses:*

All safety data will be summarized and listed for all treated subjects. All on-study AEs, SAEs, treatment-related AEs, and treatment-related SAEs will be summarized using worst grade per NCI CTCAE v4.0 by system organ class and preferred term. On-study lab abnormalities including hematology, chemistry, liver function, thyroid function, and renal function will be summarized using worst grade per NCI CTCAE v4.0 criteria.

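### Time to resolution has no rule for death and is limited to Grade 3-4 in one section only, so for the outcome of all Grade 3-5 select AEs the planned median is biased short.

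*Combined protocol and SAP*

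**What the plan says.** Section 1.3.2 sets the objective to "characterize the outcome of all high grade (CTCAE v4.0 Grade 3-4 and Grade 5) select adverse events". Section 8.3.2 measures it by three items:

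- Incidence, which names Grade 5: "incidence for high grade (Grade 3-4 and Grade 5) select adverse events".
- Timing, which for resolution does not: "median time to onset, median time to resolution (Grade 3-4". The synopsis has the same restriction: "median time to onset, median time to resolution (Grade 3-4) of the select adverse events".
- Use of immune modulating or hormonal treatment. Section 8.4.3 applies this to subjects with Grade 3-4 and Grade 5 events.

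For the timing analysis, Section 8.4.3 plans "median values using the Kaplan-Meier (KM) product-limit method with 95% CI using Brookmeyer and Crowley method of time to onset and time to resolution". It states no grade limit. Time to resolution runs from AE onset to AE end date, and the only censoring rule is: "If an AE is ongoing at the time of analysis, the time to resolution will be censored at the last contact date". Death is not mentioned. By contrast, the definitions of PFS and duration of response in Section 8.3.3 do say how death from any cause is handled.

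**The concern.** Amendment 04 added 500 subjects partly to clarify how well the toxicity management algorithms work (Section 1.1.1). Time to resolution is the planned statistic closest to that question. If subjects who die unresolved are left out of it, or treated as still able to resolve, it describes the survivors while appearing to describe everyone with a high-grade event. The treatment-use measures would cover Grade 3-5 and resolution only Grade 3-4, so the two would not share a denominator.

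Fatal select events are foreseeable. On the prior Phase 1 study, Section 1.1 says most high-grade events resolved, then adds: "One exception was Grade 4 pneumonitis considered to have led to death of three subjects". Deaths from cancer during an ongoing Grade 3-4 event meet the same gap. Section 1.4.2 cites historical second-line median survival of about 6.7 to 8.3 months.

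**Working it through.** **Plan's own figures.** The documents give no figure for time to resolution. The only precision figures are exact confidence intervals for incidence in Section 8.1, and these reproduce by Clopper-Pearson: 4/780 gives 0.14% to 1.31%, and 16/780 gives 1.18% to 3.31%. They do not bear on resolution.

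**What can happen to a subject who dies unresolved.**

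1. The event is graded 5 and falls outside the Grade 3-4 set of Section 8.3.2.
2. The event is kept, under Section 8.4.3 or because it was graded 3-4, and is censored at last contact as ongoing.
3. The death date is entered as the AE end date and counts as a resolution. Nothing in the text rules this out.

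**Direction.** Let f be the fatal share and F(t) the distribution of resolution time in non-fatal cases. The proportion of all high-grade cases resolved by time t is (1 − f)F(t), which cannot exceed 1 − f. Dropping fatal cases estimates F(t), which is larger. Censoring them shifts their weight to subjects still at risk, so 1 − KM is also at or above (1 − f)F(t). For any f above zero, the median from route 1 or 2 is too short for the full set.

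**Size.** The documents give neither f nor the times, so these are assumptions: exponential times, median 6 weeks to resolution in non-fatal cases, and median 4 weeks to death in fatal cases. With k = f/(1 − f):

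- Dropped: median = 6.
- Censored at death: the resolution hazard among those at risk gives KM survival [(1 + k)/(2^(t/12) + k)]². Setting this to 0.5 gives t = 12 × log2(√2(1 + k) − k).
- Death as non-resolution: (1 − f)F(t) = 0.5 gives t = −6 × log2(1 − 0.5/(1 − f)).

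Worked at f = 3/19:

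- Censored: k = 3/16 = 0.1875; √2 × 1.1875 − 0.1875 = 1.492; log2 = 0.577; × 12 = 6.9 weeks.
- Non-resolution: 0.5/(16/19) = 0.594; 1 − 0.594 = 0.406; −log2 = 1.300; × 6 = 7.8 weeks.

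| Fatal share f | Dropped (weeks) | Censored (weeks) | Death as non-resolution (weeks) | Most that can resolve |
|---|---|---|---|---|
| 5% | 6.0 | 6.3 | 6.5 | 95% |
| 3/19 = 16% | 6.0 | 6.9 | 7.8 | 84% |
| 1/3 = 33% | 6.0 | 8.4 | 12.0 | 67% |

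**Where the shares come from.** 5% is a low case. 3/19 divides the three prior deaths by the 19 of 306 subjects with Grade 3-4 treatment-related select AEs in Table 1.1-1, and assumes the deaths lie within the 19; its exact 95% interval is 3% to 40%. One third corresponds to the two NSCLC deaths over about six NSCLC subjects (5% of 129), again assuming they lie within that count.

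**Sensitivity to time to death.** If fatal cases die at the same rate as others resolve, the censored median is 6/(1 − f): 7.1 weeks at 3/19 and 9.0 at one third. The other two columns do not change.

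**The case against.** The other side has several fair points.

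- **The routes are inferred.** Worst grade is written for tabulation: "High grade (Grade 3-4 and Grade 5) select adverse events will be tabulated using worst grade per NCI CTCAE v4.0 criteria". It is not stated as the rule that selects events for the resolution analysis. The censoring sentence concerns events that are ongoing and does not say whether an event ending in death is ongoing. This stands: the defect is an unstated rule. But routes 1 and 2 both shorten the median, and route 3 would count a death as a resolution.
- **Deaths are not hidden.** Grade 5 incidence is reported, Grade 5 stays in the treatment-use measures, and deaths are summarised under Section 8.3.3. This also stands, but it does not correct the resolution estimate.
- **The restriction is disclosed, and a median among non-fatal events is a legitimate description.** True, but it does not meet an objective that names Grade 5, and Section 8.4.3 does not repeat the restriction.
- **Only medians are planned.** No Kaplan-Meier proportion resolved is specified, so the criticism is of the median and not of an inflated percentage.

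A reader might infer something stronger from Section 1.1 and Table 1.1-1. The three deaths were at 1 and 10 mg/kg, and the table shows four Grade 3-4 pneumonitis cases, two at each of those doses; so three of four would drop out. The documents do not support this. Section 1.1 calls the fatal cases Grade 4. If they are among the four, they sit inside a Grade 3-4 set and would not leave it; if they were graded 5, they are not among the four. The counts also mix tumor types, and the 3 mg/kg column shows no Grade 3-4 pneumonitis in 54 subjects. The same caution applies to 3/19: it serves here only as a plausible fatal share, and cases graded as they were then would fall under the censored column.

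**Conclusion.** The concern holds as an incomplete and inconsistent definition with a known direction of bias. Sections 8.3.2 and 8.4.3 differ on which grades are included, neither says what happens at death, and the likely handling understates time to resolution for the group the objective names.

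On the assumed times, the understatement against death as non-resolution is 0.2 to 0.5 weeks at 5% fatal, 0.9 to 1.8 weeks at 16%, and 3.6 to 6.0 weeks at 33%; the smaller figure is for censoring and the larger for dropping. For select events pooled, a modest shift is the reasonable expectation. For pneumonitis, the category in which the prior study's deaths occurred, it could be large, but the documents do not allow a firm figure. Deaths from other causes during an ongoing event would add to the gap and are not quantified here. No test or decision rule depends on this endpoint, so the consequence is a misleading description and not a wrong formal conclusion.

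**What to change.** In Section 8.3.2, Section 8.4.3 and the synopsis:

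- Define the resolution analysis on all subjects with a Grade 3-5 select AE, in the same words in all three places.
- Estimate the cumulative incidence of resolution with death from any cause as a competing event. Censor only subjects alive and unresolved at last contact. State that a death date never counts as a resolution date. Give the time at which the curve reaches 50%, or say that it does not.
- Report the numbers resolved, ongoing and died for each select-AE category.
- Keep any Grade 3-4 Kaplan-Meier median only as a supplementary figure, labelled as conditional on non-fatal events.

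The cost is wording and a little more analysis work. AE onset and end dates and survival status are already collected (Sections 3.6 and 8.4.3, Table 5.1-3), so no new data are needed. The resolution figures will look less favourable.
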